4.2 Other Study assessments

- Number of identified CF ablation targets
- Max #of active RF 192 electrodes during initial mapping procedure
- AAD use post the 3-month blanking period
- Incidence of repeat ablation procedures for AF post the 3-month blanking period

- Procedural data:
 - All target sites for RF lesion application
 - Location of ablation targets
 - Number of RF applications per target
 - Total RF duration per application
 - RF ablation parameters (including but not limited to: power, contact force, impedance, flow rate, temperature)
 - Total fluoroscopy time and dose
 - Total procedure, mapping and ablation time

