6.3.1 Baseline Mapping Sequence

All eligible subjects will undergo the CARTOFINDER™ Mapping Procedure, using the RF-192 catheter. The subject must be in AF prior to the insertion of the RF-192 Mapping catheter. If the subject is not in AF at the time of the procedure the patient will be regarded as discontinued per inclusion criteria, followed for 7-days post-procedure and exited from the study.

- Standard Fast Anatomic Mapping (FAM) procedure of the Right Atria (RA) using the THERMOCOOL SMARTTOUCH™ or SMARTTOUCH® SF Catheter.
- Baseline CARTOFINDER™ map, recording of the RA using the RF-192 catheter
 - On deployment of the RF-192 catheter, the basket catheter will be placed in optimal position to maximize contact with the RA wall
 - Once the catheter's position is confirmed and contact is optimal, the investigator will obtain intra-cardiac signals
 - One 30 second recording will be obtained

DO NOT perform any RA ablations at this point

- Transseptal Puncture
- Standard FAM of the Left Atria (LA) using the THERMOCOOL® SMARTTOUCH™ or SMARTTOUCH® SF Catheter.
- Baseline CARTOFINDER™ map, recording of the LA using the RF-192 catheter
 - On deployment of the RF-192 catheter, the basket catheter will be placed in optimal position to maximize contact with the LA wall
 - Once the catheter's position is confirmed and contact is optimal, the investigatorinvestigator will obtain intra-cardiac signals
 - One 30 second recording will be obtained

RF192 catheter must not remain in the subject (being deployed in the atrium) for cumulative duration greater than 1.5 hours (90 mins)

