7 DATA COLLECTION AND FOLLOW-UP SCHEDULE

7.1 Procedural Data Collection

The following procedural data will be collected:

- Mapping sequence
- Procedural flow
- Procedural time including RF ablation and mapping times
- Fluoroscopy usage
- Ablation targets and parameters
 - Areas/location of ablation targets including RAPs/Focal impulses identified by CARTOFINDER™
 - # RF applications per target
 - RF duration per application
- Cycle length
- Max #of active RF 192 electrodes
- Fluid inputs/outputs
- Subject's heart rhythm (pre-and post-ablations)
- Rate controlling medications provided inter-operatively
- Intra-Procedural complications.

- All CARTOFINDER™ maps with associated catheter locations
- Investigator feedback on quality of signal collection and mapping at the end of the procedure. The survey will contain questions to rate on a scale of 1 to 5 and will be entered into the eCRF for analysis.

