15.3.3 Investigational Device Performance

Investigational device performance will be reported as the number of ablation targets identified and the maximum % of active electrodes. Investigational device performance will also be reported by means of survey questions. Listings of survey answers/scoring will also be provided. These analyses will be conducted in the evaluable population (EP).

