18 RISK/BENEFIT ANALYSIS

18.1 Potential Risks

A degree of risk exists with the LAT Algorithm not providing accurate information on target ablation sites. This is directly related to lack of information when recordings are collected potentially due to insufficient catheter contact. Investigators (EPs) may be asked to take multiple maps for comparison but as well as have other modalities such as the EP recording system to observe real time catheter signals and fluoroscopy to determine identified target areas for clinical relevance and risk. Radiation exposure during the fluoroscopic imaging of the catheters may result in an increase in the lifetime risk of developing a fatal malignancy (0.1%) or a genetic defect in offspring (0.002%) [16, 17, 18, 19, 20, 21, 22, 23].

Do not reprocess, resterilize, or reuse. This device is packaged and sterilized for single use only. Reprocessing, resterilizing, or reusing may compromise the structural integrity of the device and/or lead to device failure that in turn may result in patient injury, illness, or death. Also, reprocessing or resterilization of single use devices may create a risk of contamination and/or cause patient infection or cross-infection, including, but not limited to, the transmission of infectious disease(s) from one patient to another. Contamination of the device may lead to injury, illness, or death of the patient.

Other potential complications, which may result from catheter insertion and manipulation as part of the prerequisite electrophysiology trial and mapping procedure, include: Allergic reaction to the local anesthetic, sedatives, X-ray dye, heparin, protamine, or other agents administered during the procedure (risk < 1%) [21, 24-27]

Arterial or venous injury, including arterial dissection, thrombosis, occlusion or hemorrhage at the catheter insertion sites or at other sites along the vessels (risk < 1%) [16, 17]. These types of injuries may cause hemorrhage, hematoma, or ischemic injury to an extremity or major organ. Hemorrhage as a result of anticoagulation (risk < 0.5%), which may require transfusion [16, 17].

Potential risk of entanglement/and or entrapment. When the RF-192 basket catheter is within the proximity of the tricuspid valve or mitral valve, cautions need to be applied to avoid entanglement with chordae tendineae.

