5.2 Other Endpoints

- Investigational Device Performance
 - Number of identified CF ablation targets
 - Max number of active RF 192 electrodes during initial mapping procedure
- AAD use post the 3-month blanking period
- Incidence of repeat ablation procedures for AF post the 3-month blanking period
- Procedural data
 - All target sites for RF lesion application
 - Location of ablation targets
 - Number of RF applications per target
 - Total RF duration per application
 - RF ablation parameters (including but not limited to: power, contact force, impedance, flow rate, temperature)
 - Total fluoroscopy time and dose
 - Total procedure, mapping and ablation time

6 Levels of Significance

No formal statistical hypothesis and inferential statistics will be formulated and performed. Two-sided 95% confidence intervals will be constructed for the effectiveness and safety endpoints.

7 Analysis Sets

The following analyses populations will be used to complete the analyses of the data:

- **Safety Subject Population (SP)**: The safety subject population will include all enrolled subjects who have the RHYTHMFINDER™ 192 Catheter inserted, regardless if CARTOFINDER guided ablation was performed.
- **Evaluable Subject Population (EP)**: The evaluable subject population will include all enrolled subjects who have the RHYTHMFINDER™ 192 Catheter inserted and where CARTOFINDER guided ablation was performed.

- **Effectiveness Subject Population (Efp):** The effectiveness subject population will include all Evaluable Subjects who meet the study eligibility criteria. Efp was not included in the protocol but added in the SAP.

8 Sample Size Justification

This is a feasibility study of safety and effectiveness in which the sample size of the clinical investigation is intended to provide preliminary estimates of these two aspects. Enrollment in the clinical investigation will be approximately 40-70 evaluable subjects.

9 Data Monitoring Committee (DMC)

No Data Monitoring Committee will be constituted for the study.

10 Analyses to be Conducted

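### RF-192 coverage is summarised only as a maximum of active electrodes, with unit and scope undefined, so poor coverage in one atrium need not show

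*Protocol*

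**What the plan says.** The coverage measure appears in five main places, and the unit changes between them.

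- Protocol 4.2 (and the synopsis): "Max #of active RF 192 electrodes during initial mapping procedure", a number.
- Protocol 7.1, the list of data to be collected: "Max #of active RF 192 electrodes", a number.
- SAP 5.2: "Max number of active RF 192 electrodes during initial mapping procedure", a number.
- Protocol 15.3.3: "Investigational device performance will be reported as the number of ablation targets identified and the maximum % of active electrodes", a percentage.
- SAP 10.4 repeats the percentage.

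Protocol 6.3.1 calls for a baseline map in each atrium. For the right it reads "Baseline CARTOFINDER™ map, recording of the RA using the RF-192 catheter", and the left has a matching step. In each chamber, "One 30 second recording will be obtained". Initial mapping therefore yields at least two recordings per subject.

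Protocol section 3 lists the functioning of the mapping catheter among the things to be assessed. Protocol 18.1 recognises that the algorithm may point to the wrong sites, and adds: "This is directly related to lack of information when recordings are collected potentially due to insufficient catheter contact". Protocol 15.3.3 restricts the device-performance analysis to the evaluable population, which 15.2 defines as subjects who had CARTOFINDER-guided ablation.

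**The concern.** A feasibility study of a new mapping catheter should show how well the basket covers each atrium, including the cases where it does badly. A maximum is the summary least able to do that. If a subject has good coverage on the right and poor coverage on the left, a maximum over both reports the right-sided value.

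The item is also open to different readings. Without a definition of an active electrode, a denominator, or the set over which the maximum is taken, two sites could enter different quantities in the same field. At stake is how a device-performance figure is read: it may look better than the coverage behind some of the maps that guided ablation. No safety or effectiveness result depends on it.

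**Working it through.** Neither document states an expected coverage, a threshold or a spread, so there is no figure to reproduce. The check has two parts.

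**1. Reading the passages together.** No section lists a count by recording or by atrium, a minimum, a mean, or a proportion below a limit. Three other sources bear on mapping quality, and none is a planned coverage summary:

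- the end-of-procedure investigator survey, scored 1 to 5 (protocol 7.1), is a subjective rating;
- the mapping-failure category (protocol 11) covers inability to record, not partial coverage;
- copies of all maps go to the sponsor (protocol 17.1), with no coverage analysis of them specified.

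Let R and L be the active fractions in the right and left atrium. If the reported value is M = max(R, L), then M ≥ L always, and M < c only when R < c and L < c. The direction follows from the definition. Extra maps, which 18.1 allows for comparison, can only raise M if they count as initial mapping.

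**2. Illustrative size.** Assumptions, none from the documents: R and L each normal with mean 70% and SD 15%, correlation ρ, and a cut-off of 60%.

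- z = (60 − 70)/15 = −0.667, so P(L < 60%) = Φ(−0.667) = 0.2525. Among the 40 to 70 evaluable subjects of protocol 15.1, that is about 10 to 18.
- Share of these that the maximum hides = 1 − P(R < 60% and L < 60%)/P(L < 60%), with the joint probability from the bivariate normal distribution. At ρ = 0 the joint probability is 0.2525² = 0.0638, and 1 − 0.0638/0.2525 = 0.75.

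| ρ | Both below 60% | Hidden share of subjects with low left atrium | Hidden subjects, n = 40 to 70 |
|---|---|---|---|
| 0 | 0.064 | 75% | 7.5 to 13.2 |
| 0.3 | 0.097 | 62% | 6.2 to 10.9 |
| 0.6 | 0.136 | 46% | 4.6 to 8.1 |
| 0.8 | 0.171 | 32% | 3.3 to 5.7 |

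The last column is n × (0.2525 − joint probability).

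A second illustration varies the rate p of poor recordings and counts subjects with at least one poor chamber. With independent chambers, P(at least one) = 1 − (1 − p)² and P(both) = p². At p = 0.10 these are 19.0% and 1.0%, so the maximum misses 18.0/19.0 = 95% of affected subjects. At p = 0.30 they are 51.0% and 9.0%, so it misses 42.0/51.0 = 82%. With a latent correlation of 0.6 the missed shares are about 76% and 60%.

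**The case against.** The strongest reply is that one value per subject is an inference. Protocol 7.1 gives a one-line item, the eCRF is still to be developed (17.1), and the table shells are in a separate document. The maximum could be the peak over time within each recording, with one value per atrium. That stands as a limit on the point. It does not remove it, because the item would still need that definition.

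Nor do the documents say that an active electrode is one in contact with the wall. It might mean one that gives a usable signal, or one that simply works. The link to contact is therefore an assumption. Protocol 6.3.1 also has the operator position the basket for best contact before recording in each atrium. This lowers the chance of a poor recording but does not measure what was achieved.

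A reader might go further in four ways that the text does not support:

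- *That 18.1 names poor contact as the cause of wrong targets.* It says only that contact is a potential reason, and it also describes safeguards: comparison maps, the EP recording system and fluoroscopy.
- *That inclusion criterion 5 calls for left-atrial coverage data.* It concerns the electrical activity of the left atrium, not how well the basket covers it.
- *That coverage can never be related to failed conversion.* The sponsor will hold the maps and may be able to recover the values. What is missing is a planned summary.
- *That a by-chamber summary alone would explain absent targets.* Subjects without guided ablation are outside the evaluable population, so the population would have to change too.

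Finally, this is an other study assessment in a descriptive study, with no coverage threshold and no decision attached to it. That is right, and it keeps the point minor.

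**Conclusion.** The point holds as a minor one. The unit mismatch and the missing definitions are plain on the text. On the natural reading, the only coverage statistic is a best case that cannot reveal poor coverage confined to one atrium, although catheter functionality is a stated aim.

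The amount of masking is unknown. The range of about 75% down to 32% rests on an assumed mean, SD, cut-off and normal shape, with correlation from 0 to 0.8. Since the same patient, operator and catheter are involved, positive correlation is plausible, and the figure for uncorrelated chambers should not be quoted alone. Only the direction is free of these assumptions, and it still depends on the maximum being taken across both atria.

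**What to change.** 1. In protocol 4.2, 7.1 and 15.3.3 and SAP 5.2 and 10.4, define an active electrode, state the denominator of the percentage, and use the same unit or units throughout.
2. Record the number and percentage of active electrodes in the analysed baseline recording, separately for the right and left atrium.
3. In SAP 10.4, summarise each chamber by median, quartiles and minimum, and add the per-subject lower of the two values. The maximum can stay as a secondary line, with its scope stated.
4. If coverage is to be related to absent targets, also summarise it in the safety population for subjects who have a baseline recording.

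The cost is about one extra eCRF field and two table rows, with a little more output if step 4 is taken up. The values may be recoverable from the maps already sent to the sponsor, without new subject procedures. The other price is a less favourable coverage figure.

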5 CLINICAL INVESTIGATION DESIGN

The study is a prospective, single arm, non randomized, open label, multicenter study.

Subjects fulfilling the inclusion / exclusion criteria and who sign the informed consent form (ICF) will be enrolled in the RAPID-AF study. The clinical investigation is targeting approximately 6-10 centers located worldwide. The study will enroll approximately 40 to 70 subjects.

This study will serve to generate a clearer perspective of the CARTOFINDER™ System's ability to generate maps for guiding ablation and the investigator's ability to maneuver, acquire signals etc. using the RF-192 catheter.

Subjects displaying an ablation target on the CARTOFINDER™ (CF) map will undergo CARTOFINDER™ Guided Ablation (CFGa) followed by PVI (WACA) ablation. Subjects not displaying an ablation target on CARTOFINDER™ will be treated per investigator's standard of care and followed up until 7 days post-procedure.

6 STUDY PROCEDURE GUIDELINES

The devices itemized below are required for this protocol, and investigational devices will be provided by the sponsor. Refer to the Table 2.3 for the status of the devices in your region.

- CARTO[®] 3 EP Navigation System, with CARTOFINDER™ Module
- CARTOFINDER™ Workstation
- RHYTHMFINDER Basket Catheter (Mapping Catheter)

Ablation catheters used for this study protocol are THERMOCOOL[®] SMARTTOUCH™ or SMARTTOUCH[®] SF Catheter (Ablation Catheter) (commercially available and used within indication for use as applicable for your country).

Biosense Webster representatives will provide training to the study site personnel in the use of the investigational devices.

Refer to the Instructions for Use for the set-up of the devices and respective connections.

6.1 Screening and Informed Consent

Subjects presenting to the institution with Persistent Atrial Fibrillation and considered for an ablation procedure should be screened by the investigator or designated member of the research team for study eligibility per the protocol inclusion and exclusion criteria.

The study investigator or designated member of the research team will obtain written informed consent from the subject. The background of the proposed study and the potential benefits and risks of the study should be explained to the subject. The subject or legal representative must sign the consent form prior to any study-specific exams or tests are provided to them that fall outside of the standard of care. The consent form used must have prior approval from the study site's Research Ethics Board/ Institutional Review Board / Ethics Committee. Failure to obtain informed consent renders the subject will be deemed ineligible for participation in the study.

Each subject screened for enrollment in the clinical investigation who signs the patient informed consent form will be enrolled into the study.

6.2 Baseline /Pre-Procedure Assessments

Pre-procedure assessments and data collection must be performed within 30 days prior to the ablation procedure unless otherwise noted.

- Demographics
- Medical history
- Arrhythmia history
- Cardiovascular medication including anticoagulation regimen
- Electrocardiogram (12-Lead ECG)
- INR (prior to ablation procedure), when applicable
- CHADS-VASC2 Score
- NYHA assessment
- Imaging (i.e. TTE) to determine the atrial size (if the subject has undergone an imaging procedure within the last 6-months where the atrial size was assessed, the pre-procedure imaging assessment is not required)
 - If left atrial size exceeds 47 mm on TTE, left atrial volume should be measured.
- Imaging for detection of LA thrombus is mandatory within 24 hours prior to ablation procedure. The imaging method used is at the discretion of the investigator and institution standard practices:
 - Transesophageal Echocardiogram (TEE)
 - Intracardiac Echocardiography (ICE)
 - Computed Tomography (CT)
 - Magnetic Resonance Imaging (MRI)
- Pregnancy test must be done on pre-menopausal women only, within 1-week of the procedure and documented in the subject's medical chart.

Subjects who signed the informed consent form and who meet all inclusion and no exclusion criteria

at screening/baseline will undergo a CARTOFINDER™ (CF) baseline map using the RHYTHMFINDER™ 192 Catheter

6.3 Baseline/Pre-procedure CARTOFINDER™ (CF) mapping:

Subjects will arrive to the electrophysiology laboratory for their clinically indicated ablation procedure and will undergo preparation for the ablation procedure according to the hospital's standard protocol (discretion of investigator), CARTO3 navigational and electro-anatomical mapping system. CARTOFINDER™ System is connected to CARTO®3 workstation with Ethernet cable for file sharing as per Instruction For Use (IFU).

6.3.1 Baseline Mapping Sequence

All eligible subjects will undergo the CARTOFINDER™ Mapping Procedure, using the RF-192 catheter. The subject must be in AF prior to the insertion of the RF-192 Mapping catheter. If the subject is not in AF at the time of the procedure the patient will be regarded as discontinued per inclusion criteria, followed for 7-days post-procedure and exited from the study.

- Standard Fast Anatomic Mapping (FAM) procedure of the Right Atria (RA) using the THERMOCOOL SMARTTOUCH™ or SMARTTOUCH® SF Catheter.
- Baseline CARTOFINDER™ map, recording of the RA using the RF-192 catheter
 - On deployment of the RF-192 catheter, the basket catheter will be placed in optimal position to maximize contact with the RA wall
 - Once the catheter's position is confirmed and contact is optimal, the investigator will obtain intra-cardiac signals
 - One 30 second recording will be obtained

DO NOT perform any RA ablations at this point

- Transseptal Puncture
- Standard FAM of the Left Atria (LA) using the THERMOCOOL® SMARTTOUCH™ or SMARTTOUCH® SF Catheter.
- Baseline CARTOFINDER™ map, recording of the LA using the RF-192 catheter
 - On deployment of the RF-192 catheter, the basket catheter will be placed in optimal position to maximize contact with the LA wall
 - Once the catheter's position is confirmed and contact is optimal, the investigatorinvestigator will obtain intra-cardiac signals
 - One 30 second recording will be obtained

RF192 catheter must not remain in the subject (being deployed in the atrium) for cumulative duration greater than 1.5 hours (90 mins)

6.4 Analysis of the CARTOFINDER™ Baseline Map

After completion of the CARTOFINDER™ baseline mapping procedure, the CARTOFINDER™ maps will be

processed and analyzed for the presences of ablation targets including FI/RAPs by the treating/ablating investigator who has been trained by Biosense Webster personnel knowledgeable in analyzing CF maps and the operation of the CARTOFINDER™ system.

Ablation Targets (FI/RAP) identification:

- Identify areas with ablation targets including focal impulse (FI) or repetitive activation patterns (RAPs)
 - If an ablation target is identified, the subject will receive CFGA followed by PVI
 - If no CF ablation target is identified, the subject will be treated per standard of care and exits the study after 7 day follow up.

No RF ablation should occur prior to analysis of the CARTOFINDER™ Maps.

6.4.1 CARTOFINDER™ Guided Ablation

All subjects will undergo CARTOFINDER™ Guided Ablation procedure followed by PVI.

- Confirm identified ablation targets on the Baseline CF map
- Ablate areas using the THERMOCOOL® SMARTTOUCH™ or SMARTTOUCH® SF Catheter identified by the CARTOFINDER™ map
 - If a post CFGA map is performed on the ablated atrium(a), analysis of the post-CFGA CF map for the existence of ablation targets should be performed
- Complete above steps until one of the following conditions is met:
 - No further ablation targets are identified on the CF Map
 - Subject achieves normal sinus rhythm or an atrial tachycardiaThe final decision to not further ablate remaining RAP/FIs regardless of above criteria being met or not, remains at investigator's discretion.
- After performing any CFGA, a CF map may be created at the investigator's discretion, but is not required.
- If subject is in AF (or other arrhythmia) after CFGA, no cardioversion is permitted.

RF192 catheter must not remain in the subject (being deployed in the atrium) for cumulative duration greater than 1.5 hours (90 mins)

6.4.2 PVI Ablation:

All subjects enrolled in the study will undergo the following PVI procedure as outlined below.

1. Pulmonary Vein Isolation will be performed using Wide Area Circumferential Ablation (WACA)

technique per the institution's standard practice.

2. Confirmation of complete entrance block must be performed after the WACA

- ⇒ *If NSR is achieved through PVI, no further ablations are permitted other than to complete the PVI.*
- ⇒ *If AT is achieved, additional ablations are permitted to ablate the Atrial Tachycardia at the investigator's discretion.*
- ⇒ *If AFL is achieved, the placement of additional RF lesions (i.e. Linear lesions at the cavotricuspid isthmus) is at the discretion of the investigator*

Prophylactic ablation of empirical sites is not allowed per protocol.

All linear lesions, if any, require confirmation of conduction block by pacing and/or mapping maneuvers

3. Perform a final CF Map* within the same atrium (a) in which the baseline map was collected.

**AT: once achieved, one "post" ablation CF map is required*

**NSR: a "post" ablation CF map is at the discretion of the investigator*

4. If subject in AF/AFL/AT after completing ablations, cardioversion may be performed at the discretion of the investigator ONLY after completing all ablations.

